6.4 Definition of Evaluable Subjects

For the primary analysis of $\Delta V_{O_2\text{peak}}$, patients with measurements at baseline are evaluable.

6.5 Early Study Termination

This study can be terminated at any time for any reason by the Duke PI-sponsor. If this occurs, all subjects on study should be notified as soon as possible. Additional procedures and/or follow up should occur in accordance with Section 9.11, which describes procedures and process for prematurely withdrawn subjects.

7 STUDY DRUG

7.1 Names, Classification, and Mechanism of Action

[figure not shown]
Enzalutamide (Xtandi®, formerly MDV3100) is an androgen receptor signaling inhibitor.

7.2 Packaging and Labeling

Drug Substance

Compound Number: MDV3100
 International
 Nonproprietary Name: enzalutamide
 Molecular Formula: C₂₁H₁₆F₄N₄O₂S
 Chemical Name: 4-[3-[4-Cyano-3-(trifluoromethyl)phenyl]-5,5-dimethyl-4-oxo-2-sulfanylideneimidazolidin-1-yl]-2-fluoro-N-methylbenzamide

Chemical Structure of Enzalutamide

Molecular Weight: 464.44
 Appearance: White crystals
 Solubility: Practically insoluble in water
 Hygroscopicity: Not hygroscopic

Drug Product

Ingredients: Enzalutamide is provided as liquid filled soft gelatin capsules for administration. Each capsule contains 40 mg of enzalutamide. The inactive ingredients are caprylocaproyl polyoxyglycerides (Caprylocaproyl macrogolglycerides [European Pharmacopoeia]), butylated hydroxyanisole, butylated hydroxytoluene, gelatin, sorbitol sorbitan solution, glycerin, purified water, titanium dioxide and iron oxide black

Appearance: Opaque white to off-white oblong liquid filled soft gelatin capsule
 Packaging: Capsules are packaged in bottles with child-resistant caps or 4- to 5- week supply in blister packs.
 Storage and Handling: Store at room temperature (≤ 25°C). For more information please follow the storage instructions provided on the drug product label.

7.3 Supply, Receipt, and Storage

Enzalutamide 40 mg capsules are supplied as white to off-white oblong soft gelatin capsules imprinted in black ink with MDV (this may be updated to ENZ depending on when the trial begins). Enzalutamide capsules are available in the following package sizes:

- Bottles of 120 capsules (NDC 0469-0125-99)

Recommended storage: Store enzalutamide capsules at 20°C to 25°C (68°F to 77°F) in a dry place and keep the container tightly closed. Excursions permitted from 15°C to 30°C (59°F to 86°F).

Medivation will manage the packaging and distribution activities for this protocol for the product enzalutamide (Xtandi®) to Duke and sub-site(s).

7.4 Dispensing

At Duke, enzalutamide will be dispensed by the Duke Investigational Chemotherapy Service (ICS) in accordance with usual ICS policy and practice. Dispensing at subsite(s) will be by the ICS-equivalent, in accordance with usual ICS-equivalent policy and practice. Subjects will be provided with a diary in which to record their intake of study drug. However, the actual number of tablets taken by the subject must be calculated from the number of tablets dispensed and returned (see below).

7.5 Compliance, Accountability, Reconciliation, and Return

Regulatory agencies require accounting for the disposition of all investigational drugs received by each clinical site. Information on drug disposition required by law consists of the date received, date administered, quantity administered, and the subject to whom the drug was administered. The site investigator is responsible for the accounting for all unused test articles and all used test article containers. The investigator uses this information to maintain an accurate and complete dispensing and inventory record.

The study drug, enzalutamide, will be provided by Medivation/Astellas, Inc. and distributed by them to all sites. The DCI monitoring team will perform drug accounting during monitoring visits. At the completion or termination of the study, a final drug accountability review and reconciliation must be completed. Any discrepancies must be investigated and their resolution documented. Instructions for this are provided as a separate attachment.

The site may destroy partially used or empty enzalutamide containers once the monitor completes the accountability of the test article. Test article destruction must be documented on the drug inventory records.

The test article accountability, reconciliation, and return procedures also apply to all test articles that are required by the protocol and supplied by the sponsor.

8 SUBJECT ELIGIBILITY

8.1 Inclusion Criteria

1. Male age \geq 18 years.
2. Histologically-confirmed adenocarcinoma of the prostate.
3. Completion of appropriate prior treatment with local therapy (i.e., prostatectomy, radiation therapy or equivalent), per NCCN Guidelines.⁸⁶
4. Detectable PSA, defined as PSA \geq 0.01 ng/ml
5. Appropriate for treatment with ADT in the opinion of the treating physician.
6. Serum total testosterone \geq 150 ng/dL (5.2 nmol/L).
7. ECOG performance status of \leq 1 (Appendix A)
8. Planned treatment with castration therapy (GnRH agonist/antagonist) for \geq 8 months.
9. Must not have any of the following absolute contraindications to cardiopulmonary exercise testing and/or aerobic training as determined by the attending oncologist:

Absolute Contraindications

 - Acute myocardial infarction (within 3-5 days of any planned study procedures)
 - Unstable angina
 - Uncontrolled arrhythmia causing symptoms or hemodynamic compromise
 - Recurrent syncope
 - Active endocarditis
 - Acute myocarditis or pericarditis
 - Symptomatic severe aortic stenosis
 - Uncontrolled heart failure
 - Acute (within 3 months) pulmonary embolus or pulmonary infarction
 - Thrombosis of lower extremities
 - Suspected dissecting aneurysm
 - Uncontrolled asthma
 - Pulmonary edema
 - Room air desaturation at rest \leq 85%
 - Respiratory failure
 - Acute non-cardiopulmonary disorders that may affect exercise performance or be aggravated by exercise (i.e. infection, renal failure, thyrotoxicosis)
 - Mental impairment leading to inability to cooperate.
10. Able to swallow enzalutamide and comply with study requirements.
11. Must be able to complete an acceptable cardiopulmonary exercise test (CPET) at baseline (see Section 9), defined as at least one of the following:
 1. Achieving a plateau in oxygen consumption concurrent with an increase in power output;
 2. Respiratory exchange ratio \geq 1.1 (RER);
 3. Volitional exhaustion with a rating of perceived exertion \geq 17 (RPE)
12. Must be able to complete an acceptable muscular strength test (assessed using calculated one-repetition maximum (1-RM)) at baseline (see Section 9), in the opinion of the fitness specialist, exercise physiologist, or trained designee administering the test.
13. Life expectancy of \geq 12 months.
14. Must use a condom if having sex with a pregnant woman.
15. Male subject and his female partner who is of childbearing potential must use 2 acceptable methods of birth control (one of which must include a condom as a barrier method of contraception) starting at screening and continuing throughout the study period and for 3 months after final study drug administration. Two acceptable methods of birth control thus include the following:
 - Condom (barrier method of contraception);

AND

One of the following is required:

- Established use of oral, or injected or implanted hormonal method of contraception by the female partner;
- Placement of an intrauterine device (IUD) or intrauterine system (IUS) by the female partner;
- Additional barrier method: Occlusive cap (diaphragm or cervical/vault caps) with spermicidal foam/gel/film/cream/suppository by the female partner;
- Tubal ligation in the female partner;
- Vasectomy or other procedure resulting in infertility (e.g., bilateral orchiectomy), for more than 6 months

16. Subjects must have normal organ and marrow function as defined below:

- absolute neutrophil count >1,500/ μ L
- platelets >100,000/ μ L
- total bilirubin <2.5 X institutional upper limit of normal
- AST(SGOT)/ALT(SGPT) <2.5 X institutional upper limit of normal
- Creatinine \leq 2.0 OR creatinine clearance >30 mL/min/1.73 m² for subjects with creatinine levels above institutional normal.

8.2 Exclusion Criteria

1. Definite evidence of metastatic prostate cancer, in the opinion of the treating physician. Pelvic and retroperitoneal lymph nodes < 2.0 cm in short axis are allowed.
2. Subjects who have had treatments with GnRH agonists/antagonists and/or anti-androgens within 1 year of randomization.
3. Use of herbal products that may have hormonal anti-prostate cancer activity and/or are known to decrease PSA values (e.g., saw palmetto) or systemic corticosteroids for prostate cancer within 4 weeks of day 29 visit (start of Enzalutamide and ADT).
4. Subjects who have had radiotherapy within 12 weeks prior to entering the study or those who have not recovered from adverse events due to agents or therapies administered for treatment of prostate cancer more than 4 weeks earlier (except urinary, rectal, and sexual side effects related to prostatectomy or radiotherapy are permitted)
5. Subjects who have had any surgical procedure (i.e. TURP, etc.) within 4 weeks prior to entering the study.
6. Subjects who are receiving any other investigational agents.
7. Significant cardiovascular disease, including:
 - Symptomatic left ventricular dysfunction or known baseline left ventricular ejection fraction (LVEF) by multigated acquisition scan (MUGA) or echocardiogram (ECHO) of < lower limit of institutional normal (LLN). "Symptomatic" is defined as New York Heart Association (NYHA) Class II or greater. Note: MUGA and ECHCO do NOT need to be measured to establish eligibility for this study.
 - Uncontrolled hypertension (in the opinion of the treating provider).
 - Myocardial infarction, severe angina, or unstable angina within 6 months prior to administration of first dose of study drug.
 - History of serious ventricular arrhythmia (i.e., ventricular tachycardia or ventricular fibrillation) within 12 months of first dose of study drug.
 - Uncontrolled cardiac arrhythmias.
 - Coronary or peripheral artery bypass graft within 6 months of first dose of study drug.
 - History of CVA, TIA, or rest claudication within 6 months of first dose of study drug.
8. Uncontrolled intercurrent illness including, but not limited to, ongoing or active infection, symptomatic congestive heart failure, unstable angina pectoris, cardiac arrhythmia, or psychiatric illness/social situations that would limit compliance with study requirements (in the opinion of the treating provider).
9. Subjects with any condition (e.g., gastrointestinal tract disease resulting in an inability to take oral medication or a requirement for IV alimentation, prior surgical procedures affecting absorption, or active peptic ulcer disease) that impairs the ability to swallow and retain enzalutamide are excluded.
10. History of another invasive cancer within 5 years of randomization with the exceptions of (a) non-melanoma skin cancers and (b) American Joint Committee on Cancer (AJCC) Stage 0 or 1 cancers that have

a remote probability of recurrence, in the opinion of the treating physician, in consultation with the principal investigator.

11. Known or suspected brain metastasis or leptomeningeal disease.
12. History of seizure or any condition that may predispose to seizure (e.g., prior cortical stroke, significant brain trauma) at any time in the past. Also, history of loss of consciousness or transient ischemic attack within 12 months of the Day 1 visit.

9 SCREENING, REGISTRATION, AND ON-STUDY TESTS AND PROCEDURES

In addition to assessment for the **primary** endpoint (VO₂peak) by cardiopulmonary exercise testing (CPET), **secondary** and **exploratory** assessments for functional capacity, quantitative skeletal muscle function, metabolic, patient-reported outcomes, PSA, and metabolomics endpoints will occur throughout the study as specified below in the Schedule of Events.

The important time periods during the study include:

- **Screening** on Day -42 to randomization
- **Exercise Testing on Day -30 to randomization**
- **Randomization on Day -14 to Day 1, but after exercise testing (specifically, CPET) is complete**
- **Lead-In** of Usual Care (UC) or Exercise Training starting on Day 1
- **Treatment Period 1:** Enzalutamide + ADT with either UC or Exercise Training from Day 29 to 113
- **Treatment Period 2:** Enzalutamide + ADT from Day 114 to 252
- **End of treatment/Safety Follow-Up** within 30 days after the last dose of enzalutamide or prior to initiation of cytotoxic or investigation therapy, whichever occurs first

All subjects will receive treatment with ADT + enzalutamide for 32 weeks.

In addition, subjects randomized to Exercise Training (Arm B) will undergo a 16 week combined aerobic and resistance exercise training program, including a 4 week Lead-In before starting therapy with ADT + enzalutamide and during the first 12 weeks of therapy with ADT + enzalutamide.

SCHEDULE OF EVENTS

Phase		Screen	Baseline Exercise Testing ^{c,p}	4 Week Lead-In ^p		Treatment Period 1: Enzalutamide + ADT +/- Exercise Training				Treatment Period 2: Enzalutamide + ADT and Safety Follow-up	Unscheduled Visit ^a
				2	3	4					
Clinic Visit Number		1				2	3	4	5 (EOT) SEE NOTE		
Day		-42 to randomization	-30 to randomization	1 ^q	22	29	57	64	113	252	
Week		-6 to -1		1	4	5	9	10	17 ^a	37 ^a	
Window (Days)		NA		NA	+6	±3	±7	±3	±7	-7, +30	NA
General Evaluations	See Section										
Informed Consent ^b	9.2.1	X									
Eligibility Criteria	8	X									
Medical History	9.12.1	X									
Randomization ^c	6.1.4			X ^c							
Physical Exam ^d	9.12.2	X				X	X		X	X	X
Height, Weight, BMI	9.12.2	X				X	X		X	X	X
Vital Signs ^e	9.12.2	X				X	X		X	X	X
Performance Status (ECOG) ^f	App. A	X				X	X		X	X	X
Concomitant Medications	6.1.3	X				X	X		X	X	X
Adverse Events ^g	10	X				X	X		X	X	X
Laboratory Evaluations											
CBC with platelets ⁱ	9.1-9.7	X ⁱ				X	X		X	X	X ^h
Serum Chemistry ⁱ	9.1-9.7	X ⁱ				X	X		X	X	X ^h
Disease Evaluations											
PSA ^{j,b}	j, k	X ^k	X ⁱ			X	X		X	X	X ⁱ
Testosterone		X					X		X	X	
CT and bone scans ^{k,l}	k,l	X ^{k,l}									
Correlative Evaluations											
CPET	9.12.3		X			X			X		
Chair Stand	9.12.3		X						X		
Timed Up and Go	9.12.3		X						X		
6 min walk distance (Duke patients only)	9.12.3		X						X		
Musc. Strength ⁿ	9.12.3		X		X ^q			X ^q	X		
Muscle CSA ^s (protocol v1-v15 only)	9.12.3		X						X		
Musc. Endur. ⁿ	9.12.3		X		X ^q			X ^q	X		
FACT-P	9.12.3		X						X	X	
FACIT-Fatigue	9.12.3		X						X	X	
Godin Leisure Time Exercise	9.12.3		X						X	X	
Food Frequency Questionnaire	9.12.3		X						X		

Fasting glucose, insulin, HgbA1C ^s (protocol v1-v15 only)	9.12.3		X					X		
Body Composition ^r	9.12.3		X					X		
Metabolomics	9.12.3		X				X	X		
Treatment										
Exercise Training (ARM B ONLY) ^p	9.5-9.6			X	X	X	X	X		
Enzalutamide	9.6					X	X	X	X	
ADT ^m	9.6					X	X	X		

NOTE: The Safety Follow-Up visit will occur in conjunction with the End of Treatment visit 30 days after the last dose of enzalutamide or prior to initiation of cytotoxic or investigational therapy, whichever occurs first.

- a. Unscheduled visits may be performed at any time during the study as clinically indicated to assess for or follow-up on adverse events. Unscheduled visits may also occur due to holidays or other scheduling difficulties and in between week 17 and week 37 as clinically indicated.
- b. Informed consent may be performed within 42 days prior to enrollment (Day 1), but must be obtained prior to the performance of any study-specific procedures.
- c. Randomization should be performed within 30 days after baseline testing (specifically, CPET) is completed, but only after eligibility is confirmed and up to 14 days prior to Day 1. **See also footnote p. below.**
- d. A complete physical examination is required at the Screening, Day 113, and Day 252 visits. A brief symptom-directed physical examination should be performed at all other clinic visits.
- e. Vital signs (temperature, blood pressure, heart rate) are to be obtained at each visit.
- f. Performance status by Eastern Cooperative Oncology Group (ECOG) scoring (**Appendix A**).
- g. Exercise-related adverse events will be collected from baseline/screening through the End of Study visit for all subjects. All other adverse events will be collected from the start of study drug. Serious adverse events are recorded from the time the informed consent form is signed until the Safety Follow-Up visit (or screen failure). In the event of no Safety Follow-Up visit, adverse event information will be collected through 30 days after the last dose of study drug. Subjects should be contacted by phone for adverse event follow-up if they do not come to the clinic for the Safety Follow-Up visit.
- h. Clinical laboratory tests may be performed at unscheduled visits if clinically indicated.
- i. Labs performed as part of screening are good for 30 days before randomization and do not need to be repeated.
- j. PSA may be performed at Unscheduled Visits as indicated to confirm PSA progression. No subject should discontinue study drug due to PSA rise during the first 12 weeks of therapy. Subjects with PSA progression on or after Week 17 must have progression confirmed by a second consecutive assessment conducted at least 3 weeks later before study drug discontinuation.
- k. CT of the abdomen and pelvis and bone scans should be performed to document that there is no definite evidence of metastatic disease at the time of screening. MRI of the abdomen and pelvis may be used in place of the CT.
- l. Baseline imaging performed per NCCN Guidelines⁸⁶ prior to informed consent as standard of care may be used so long as it is performed within 84 days prior to randomization.
- m. ADT (GnRH analogue) will be administered as per standard of care to maintain a castrate level of serum testosterone (<50 ng/dL) from Day 29 to Day 252.
- n. Muscular Strength and Muscular Endurance must be done at least 24 hours before or after CPET to allow adequate recovery time.
- o. Both the usual care group and the exercise training group will have a 4 week lead-in before starting ADT plus enzalutamide; only the exercise training group will undergo exercise training during this time.
- p. Day 1 is defined as the randomization day for Arm A (non-exercise) and the start of exercise for Arm B.
- q. Randomization may be done on Day 1 prior to the patient's exercise training session(s) for that week.
- r. DEXA scan for body composition should be fasting, if possible.
- s. Muscle CSA and Fasting glucose, insulin, and HgbA1C will no longer be collected starting from Protocol v16 approval (5/25/17 moving forward). This applies to subjects currently enrolled and future enrollments.

UC, usual care; ADT, androgen deprivation therapy; BMI, body mass index; ECOG, Eastern Cooperative Oncology Group; CBC, complete blood count; PSA, prostate-specific antigen; CT, computed tomography; CPET, cardiopulmonary exercise test;1-RM, 1-repetition maximum (voluntary); CSA, cross-sectional area; Musc. Endur., muscular endurance; FACIT, Functional Assessment of Chronic Illness Therapy; FACT-P, Functional Assessment of Cancer Therapy-Prostate; HgbA1c, glycosylated hemoglobin.

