5 OBJECTIVES AND ENDPOINTS

All endpoints will be evaluated at the time points specified in the Schedule of Events at the beginning of **Section 9**. See **Section 12** for Statistical Methods and Data Analysis. Key comparisons will be the change from Day 1 (week 1) to Day 113 (week 17), which corresponds to the end of the 16 week exercise training program for Arm B, and from Day 1 (week 1) to Day 252 (week 37), which corresponds to the end of the 32 weeks of treatment with enzalutamide and ADT for both Arms.

	Objective	Endpoint	Analysis
Primary	Compare cardiopulmonary function in usual care vs. exercise training arms	Change in $\text{VO}_{2\text{peak}}$ with usual care or exercise training at 16 weeks from baseline	See Section 12.1 to 12.4
Key Secondary	Compare the effects on physical functioning / functional capacity	Objective assessments (i.e., chair-stand test, timed up and go, 6 minute walk distance) of functional capacity	See Section 12.5
Other Secondary	Compare the effects on primary physiological determinants of $\text{VO}_{2\text{peak}}$	Upper and lower extremity maximal muscular strength (voluntary one-repetition maximum [1-RM]) and muscular endurance (repetitions to fatigue at 70% of 1-RM and muscle cross sectional area of the dominant thigh (3.0 T magnetic resonance imaging)	See Section 12.5
Other Secondary	Compare the effects on metabolic outcomes of interest	Metabolic control (fasting glucose, insulin, glycosylated hemoglobin, HOMA-IR) and body composition (lean and fat body mass)	See Section 12.5
Other Secondary	Compare the effects on patient reported outcomes (PROs) of interest	Quality of Life (FACT-P), Fatigue (FACIT-F), and Leisure Time Exercise Habits (Godin Leisure Time Exercise Questionnaire)	See Section 12.5
Other Secondary	Evaluate safety, feasibility, and acceptability of exercise training	Eligibility rate, acceptance rate, adherence rate, attrition rate, and adverse event rate (CTCAE v4.0) in each arm	See Section 12.5
Exploratory	Compare PSA response rates	Maximum decrease in PSA from baseline (waterfall plot)	See Section 12.5
Exploratory	Describe metabolomics changes	Targeted and untargeted metabolic profiling	See Section 12.5
Sensitivity	Assay the robustness of results observed in analyses based on the modified ITT population	Primary and Key secondary endpoints, using Last Observation Carried Forward methods	See Section 12.5

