10.1 Adverse Events

An adverse event (AE) is any untoward medical occurrence in a subject undergoing a study procedure/intervention and/or receiving study drug; which may or may not have a causal relationship with study procedures, interventions or treatments. For this protocol, the definition of AE also includes worsening of any pre-existing medical condition. An AE can therefore be any unfavorable, unintended or worsening sign or symptom (including an abnormal laboratory finding, or disease temporally associated with exercise testing for both arm A and arm B; exercise training for arm B; and/ or related to the use of enzalutamide. Abnormal laboratory findings without clinical significance (based on the PI's judgment) should not be recorded as AEs. But laboratory value changes that require therapy or adjustment in prior therapy are considered adverse events.

Research exercise-related adverse events will be collected from the baseline exercise testing to the End of Study visit (as defined in **Section 9.8**) for all subjects (Except anticipated AEs-see section 10.1.2). All subjects will have enzalutamide related adverse events collected from the start of study drug on week 5, day 29 through the Safety Follow-up visit.

Serious adverse events that are related to study exercise procedures (CPET, 1RM, Chair testing, etc) are recorded from the time the informed consent form is signed until the Safety Follow-Up visit (withdrawal or screen failure). All SAEs will be collected regardless of attribution starting once the patient takes his first dose of study drug through the Safety Follow-Up visit. All AEs and SAEs must be recorded in the subject medical record and adverse events case report form.

AEs will be assessed according to the CTCAE version 4.0. If CTCAE grading does not exist for an AE, the severity of the AE will be graded as mild (1), moderate (2), severe (3), life-threatening (4), or fatal (5).

Attribution of AEs will be indicated as follows:

- Definite: The AE is clearly related to the study drug and/or exercise training and/or exercise testing
- Probably: The AE is likely related to the study drug and/or exercise training and/or exercise testing
- Possible: The AE may be related to the study drug and/or exercise training and/or exercise testing
- Unlikely: The AE is doubtfully related to the study drug and/or exercise training and/or exercise testing

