For analysis of metabolomics, PCA analysis will be used to reduce the large number of correlated factors into a smaller number of dimensions. Unless otherwise noted, all analyses will be done separately for the usual care and exercise groups. Of primary interest is the association of metabolomic biomarkers with changes in both VO₂peak and HOMA-IR. Changes in metabolite concentrations and VO₂peak or HOMA-IR will be compared between the usual care and exercise groups using ANOVA. Correlation analysis and linear regression will be used to describe the relationship between metabolomics biomarker changes and VO₂peak or and HOMA-IR. Nominal statistical significance will be defined as p<0.05.

In addition, the maximum PSA change from baseline in each patient will be described using waterfall plots. The PSA response rate, defined as the proportion of men with a ≥80% decline in PSA from baseline, will be reported for each arm. The median decrease in PSA will also be reported for each arm.

Sensitivity analyses will be performed repeating primary endpoint and key secondary endpoint analyses using Last Value Carried Forward (LOCF) methods. The intent of this sensitivity analysis is to assay the robustness of results observed in the modified ITT population.

Adjustment for multiple comparisons is not planned for secondary or exploratory measures.

Rates of adverse events, classified by CTCAE v4.0, will be displayed by body system and preferred term for each arm.

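### Before Day 29 a non-serious AE is collected only if judged exercise-related, so the AE rate by arm is not ascertained alike in the lead-in; footnote g and Section 10.1 also conflict on AE and SAE collection

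*Combined protocol and SAP*

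**What the plan says.** Two places set the collection rules.

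- Schedule of Events (Section 9), footnote g: "Exercise-related adverse events will be collected from baseline/screening through the End of Study visit for all subjects". It continues: "All other adverse events will be collected from the start of study drug". On SAEs it says: "Serious adverse events are recorded from the time the informed consent form is signed until the Safety Follow-Up visit (or screen failure".
- Section 10.1: "Research exercise-related adverse events will be collected from the baseline exercise testing to the End of Study visit", with the anticipated events of Section 10.1.2 excepted. From Day 29: "All subjects will have enzalutamide related adverse events collected from the start of study drug on week 5, day 29". On SAEs from consent onward: "Serious adverse events that are related to study exercise procedures (CPET, 1RM, Chair testing, etc) are recorded". From the first dose, Section 10.1 collects every SAE whatever its attribution.

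The results feed a stated endpoint. Under the objective on safety, feasibility and acceptability of exercise training, Section 5 lists the "adverse event rate (CTCAE v4.0) in each arm". Section 12.5 says: "Rates of adverse events, classified by CTCAE v4.0, will be displayed by body system and preferred term for each arm". Neither section splits the display by period or by attribution.

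**The concern.** When attribution decides whether an event is recorded at all, a comparison of AE rates between arms depends on who can make the attribution as well as on what happened to the men. In the lead-in both arms are off drug and only Arm B trains. The same headache or strain can enter the data in Arm B as training-related. In Arm A it can enter only if someone ties it to an exercise test. Section 6.1.4 makes the study open label, so the judgement is made knowing the arm.

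The lead-in is also the only period in which men train without enzalutamide and ADT, so it carries the cleanest information on the safety of the exercise programme itself. Under the rule as written, the usual-care background rate for those weeks is not collected. Separately, if two sites follow two different texts on what to collect after Day 29, pooled AE tables would mix two definitions.

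**Working it through.** The plan states no AE rate, so there is no figure to reproduce. The check is a comparison of the texts, followed by a labelled illustration.

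**Texts side by side**

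| Event and period | Footnote g | Section 10.1 |
|---|---|---|
| Non-serious, before Day 29 | Exercise-related only | Exercise-related only, less anticipated events |
| Non-serious, from Day 29 | All | Enzalutamide-related, plus exercise-related to End of Study |
| Serious, before first dose | All, from consent | Those related to study exercise procedures |
| Serious, from first dose | All | All |

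The texts agree on the lead-in gate for non-serious AEs. They conflict in rows two and three.

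**Why the gate acts differently by arm**

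1. Section 10.1 links exercise testing to both arms and exercise training to Arm B only. Footnote o confirms that only Arm B trains in the lead-in.
2. The Schedule of Events has no AE assessment between screening and Day 29. Arm B has a goal of three supervised sessions a week from Day 1 (Section 9.5), so its men have more occasions to mention an event.

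**Share of follow-up affected**

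- Of the 16-week exercise programme: 28/112 = 25%.
- Of the 36 weeks to Day 252: 28/252 = 11%.

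**Illustration, on assumptions that are not in the documents**

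Assume the true rate of non-serious AEs is constant and equal in both arms. Let q be the share of Arm B's AEs during training that are judged exercise-related (taken as 0 in Arm A). Let e be the share of AEs after Day 29 judged enzalutamide-related, the same in both arms. The true B:A ratio is then 1.

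Under footnote g, the recorded B:A ratio is:

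- 16 weeks: (84 + 28q)/84. At q = 0.1 it is 86.8/84 = 1.03; at q = 0.5, 98/84 = 1.17; ceiling at q = 1, 112/84 = 1.33.
- 36 weeks: (224 + 28q)/224. At q = 0.1 it is 226.8/224 = 1.01; at q = 0.5, 238/224 = 1.06; ceiling 252/224 = 1.125.

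Under Section 10.1 read literally, over 16 weeks A = 84e and B = 28q + 84[e + (1 − e)q]:

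- e = 0.7, q = 0.1: 64.12/58.8 = 1.09.
- e = 0.3, q = 0.5: 68.6/25.2 = 2.72.

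Over 36 weeks, add 140e to each arm:

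- e = 0.7, q = 0.1: 162.12/156.8 = 1.03.
- e = 0.3, q = 0.5: 110.6/67.2 = 1.65.

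At q = 0 every ratio is 1.00. The illustration leaves out testing-related AEs in Arm A and the exception for anticipated events, both of which would lower the ratio.

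**The case against.** The strongest defence is that the plan is broader than single sentences suggest and that little rests on the display. Four stronger readings are tempting, and the documents do not support them.

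- *After Day 29 only enzalutamide-related AEs are collected.* Section 10.1 does not say only. It continues exercise-related AEs and takes all SAEs after first dose. It defines an AE without requiring causality, asks for all AEs to be entered on the case report form, and has attribution grades for unlikely and unrelated events. Footnote g collects all other AEs from Day 29. What stands is a conflict between the two texts.
- *Fatigue attributed to ADT would be missed.* Section 10.1.1 asks for fatigue and generalized muscle weakness to be identified, graded and attributed throughout the study, and footnote g would capture them from Day 29. Non-serious fatigue in Arm A during the lead-in, if not tied to testing, has no clear route in either collection rule. That belongs to the lead-in point.
- *Arm A records nothing in the lead-in.* Testing-related AEs count in both arms, and footnote g records SAEs from consent. The asymmetry is in non-serious events.
- *The rule inflates Arm B's AE rate.* The attribution gate pushes that way, but Section 10.1 excepts the anticipated events of Section 10.1.2 (soreness, joint and back pain, cramps). The exemption sentence in 10.1.2 names CPET and transient events, so its reach into training is unclear, but it could lower Arm B's counts. The net direction is not established.

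It is also fair that Section 5 says evaluate rather than compare for safety, and that Section 12.5 displays rates without a test. That limits the consequence. It does not make the lead-in data alike in the two arms.

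**Conclusion.** The point holds in two parts. First, both texts admit a non-serious AE before Day 29 only through an unblinded exercise attribution, and only Arm B has training to attribute to, so the AE rates by arm are not ascertained alike for that period. Second, footnote g and Section 10.1 conflict on non-serious AEs from Day 29 and on SAEs before first dose.

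The lead-in covers 25% of the exercise programme and 11% of the 36 weeks. The effect on the AE display cannot be sized from the documents. With no true difference, and for q from 0.1 to 0.5, the illustration gives a recorded ratio of 1.03 to 1.17 over 16 weeks under footnote g. For e from 0.3 to 0.7 and the same q, it gives 1.09 to 2.72 under the literal reading of Section 10.1. These ranges rest wholly on the assumed shares. The display is descriptive and secondary, and the VO₂peak analysis is unaffected. The change should still be made, because events not collected at the time may not be recoverable later.

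**What to change.** 1. Reconcile footnote g and Section 10.1 into one rule: all AEs and SAEs, regardless of attribution, from randomisation in both arms, with attribution kept as a recorded field on the existing scale. State in the same rule whether the 10.1.2 exemption covers training as well as CPET.
2. Ask about lead-in AEs in the same way in both arms at the Day 29 visit. Flag by source any event volunteered at a training session, since Arm B's extra contacts would otherwise keep ascertainment unequal.
3. Tabulate the lead-in, Treatment Period 1 and Treatment Period 2 separately. Count the lead-in from Day 1, because Section 9.4 lets Arm B be randomised up to 14 days before Day 1; show any earlier events apart. Show exercise-related AEs in their own table.
4. For men already enrolled, confirm which rule each site used. Compare arms from Day 29 only where all AEs were collected; a Day 29 cut does not help where a site followed the narrow reading of Section 10.1. List lead-in exercise-related AEs without an arm comparison.

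The cost is a wording amendment, one structured enquiry at a visit that already exists, and modest extra data entry.
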